5.2. Imaging Analysis

Pre-operative and post-operative imaging will be evaluated by an independent imaging core lab, and interpretative findings will be reported in the final study report.

6. BASELINE DEMOGRAPHICS

6.1. Patient Accounting

A complete accounting of NITE 1 patients will be presented in Table 6.1 entitled *Patient Accounting (NITE 1 Population)*. Listing 6.1 entitled *Patient Disposition* supports Table 6.1. This Listing will be sorted by patient number and will contain the reason for discontinuation (if applicable), along with the date of the last observation.

6.2. Baseline Demographic Factors

All patients in the NITE 1 population will be included in Table 6.2 entitled *Summary of Patient Demographics (ITT Population)*. This table summarizes the patient population with respect to gender, age in years at the time of the procedure, race, and ethnicity. Age will be summarized

using descriptive statistics. The number and percent of each gender, race, and ethnicity category will be presented using counts and percentages. The supportive data for Table 6.2 will be presented in Listing 6.2 entitled *Patient Demographics*. This listing will be sorted by patient number.

6.3. Relevant Medical History

Results will be presented based on the reported medical history for the NITE 1 population. Results will be summarized and presented in Table 6.3 entitled *Summary of the Relevant Medical History* and Table 6.3.1 *Summary of Relevant Neurological History*. The patients will be summarized using counts and percentages for those patients who had a pre-index procedure medical history and neurological history. The supportive data for this table will be presented in Listing 6.3 entitled *Relevant Medical History* and Listing 6.3.1 *Relevant Neurological History*. This listing will be sorted by patient number.

7. PROCEDURE AND TREATMENT ADMINISTRATION

This section will describe the summarization and analysis of the administration of the treatment and the exact procedure.

7.1. Summary of Procedures and Treatments

Results will include descriptive statistics for the variable collected during the procedure based on the NITE 1 population. A summary of the results will be presented in Table 6.4 entitled *Summary of Procedures and Treatments* (ITT Population). Results will be supported by the data presented in Listing 6.4 *Procedures and Treatments*, sorted by patient number and the date of procedure.

7.2. Summary of Procedures Time Metrics

Procedural time related results will be tabulated and presented in Table 6.4.1 entitled *Summary of Procedural Time Metrics*. Continuous parameters will be summarized using descriptive statistics. Results will be supported by the data presented in Listing 6.4.1 *Procedural Time Metrics*, sorted by patient number and the date of procedure.

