3.2.4 Procedural Times

The average time from skin incision to cannulation of the common carotid artery (CCA) was 13 minutes in the ROADSTER study population (excluding aborted cases). In ROADSTER 2, mean procedure time was 74.8 minutes (skin incision to skin closure). This is comparable to the mean procedure time for transfemoral CAS of 69 minutes as reported in the CREST study(Vilain et al. 2012). Procedure time was not defined in the CREST study.

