7.2 Secondary Outcomes

The following secondary outcomes will be collected and evaluated in all enrolled patients:

- Carotid access time
 - Hospital arrival to neck incision
 - Neck incision to carotid exposure
 - Neck incision to carotid artery catheterization (includes securing of sheath)
 - Neck incision to femoral venous sheath access (includes securing of sheath)
 - Neck incision to initiation of reverse flow
- Time to final revascularization
 - Hospital arrival to OR
 - Last known well to final revascularization
 - Admission to final revascularization
 - OR to final revascularization
 - Cutdown to final revascularization
 - Arterial introduction of interventional tools to final revascularization
 - Total reverse flow time (CCA clamp to CCA unclamp)

- Device-related complications
- Neurologic assessment at 90 days (proportion of patients with a nondisabling or disabling stroke according to NIHSS)
- Technical success rate – Successful introduction of endovascular tools through the NOVIS Transcarotid NPS.
- Rates of revascularization success assessed by angiographic core lab (mTICI \geq 2b)

8 Study Population

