10.3.4 Endovascular Therapy

Patients will be treated with endovascular therapy system(s) (stentriever and/or aspiration catheters) currently cleared by the FDA, under their cleared indications for use, for thrombus removal in patients experiencing an acute ischemic stroke in the anterior circulation due to large vessel occlusion. Investigators will be trained to follow the published instructions for use for the endovascular therapy system used in the procedure. Deviations from the cleared time of usage must be documented as a protocol deviation. Ensure the neurointerventional devices are labeled with an outer diameter that is compatible with the inner diameter of the NOVIS NPS Arterial Sheath and attached rotating hemostasis valve.

These devices will be introduced into the vasculature via the NOVIS NPS Arterial Sheath, during this interventional step the NOVIS NPS will be set to High Flow and remain on this setting until the neurothrombectomy has been completed.

Once the endovascular therapy systems are introduced into the NOVIS NPS Arterial Sheath continuous reverse flow will be maintained throughout the interventional steps, until all other devices are removed and the thrombectomy attempt is complete.

The transcarotid intervention may be abandoned at the discretion of the treating operator. The operator will document reason for failure in patient records and study case report forms.

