Serious Adverse Events will be tabulated and reported accordingly. The primary endpoint and all secondary endpoints will be analyzed based on both the ITT and PP population. All available data on the ITT patients who were enrolled in the study will be included. This SAP presents the data results to be reviewed in evaluating the device-related SAEs, other SAEs, and functional independence at 90 days. Secondary endpoints to be summarized include the following:

- Carotid access time
 - Hospital arrival to neck incision
 - Neck incision to carotid exposure
 - Neck incision to carotid artery catheterization (includes securement of sheath)
 - Neck incision to femoral venous sheath access (includes securement of sheath)
 - Neck incision to initiation of reverse flow
- Time to final revascularization
 - Hospital arrival to OR
 - Last known well to final revascularization

- Admission to final revascularization
- OR to final revascularization
- Cutdown to final revascularization
- Arterial introduction of interventional tools to final revascularization
- Total reverse flow time (CCA clamp to CCA unclamp)
- Device-related complications
- Neurologic assessment at 90 days (proportion of patients with a nondisabling or disabling stroke according to NIHSS)
- Technical success rate – Successful introduction of endovascular tools through the NOVIS Transcarotid NPS.
- Rates of revascularization success assessed by angiographic core lab (mTICI \geq 2b)

To determine if the NOVIS NPS patients are comparable in safety to TCAR patients using the ENROUTE NPS, the following mutually exclusive populations will be compared:

Within the ***Complete NOVIS NPS Population***: All NOVIS NPS patients who were enrolled as part of the ITT study population in the NITE 1 study.

Within the ***Complete TCAR Population***: All TCAR patients who were enrolled in the ENROUTE clinical program (PROOF, and ROADSTER studies) and underwent the procedure.

There will be two independent sets of analyses performed to assess comparability between both patient populations – one using the ITT NITE 1 study population and the second using the Per Protocol NITE study population. The research questions, datasets, methods of analysis, and summarization of the results will be discussed in this SAP. The general design of the analysis summary tables, figures, and patient data listings used to present the analysis results are also presented in this plan.

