4. STATISTICAL RATIONALE FOR THE NITE 1 FEASIBILITY STUDY

The Intent-to-Treat (ITT) population is defined as enrolled patients who have consented, meet all inclusion and none of the exclusion criteria, and in whom transfemoral therapy has been deemed a failure. The per protocol (PP) population will be comprised of patients from the ITT population AND for whom no major protocol deviations have occurred. If the deviation meets any of the following criteria, it is considered a major protocol deviation:

- changing the protocol without prior IRB approval,
- failure to obtain informed consent, or
- falsifying research or medical records

The NITE 1 study protocol aims to recruit a minimum of 30 and a maximum of 40 patients in the PP population and to be analyzed in this study, unless the study enrollment is stopped sooner due to decision by the DSMB or Sponsor. Enrollment in the ITT cohort will cease when a targeted 30 PP patients have been accrued and complete the study follow-up period. Additional patients beyond 30 who are successfully enrolled while waiting for the 30th PP patient to complete the 90-day follow-up period, will be analyzed in the cohort for which they qualify, whether PP or ITT. Enrollment will continue till a maximum of 60 patients are enrolled in the ITT population or the study enrollment is stopped by decision from the DSMB or Sponsor.

Serious Adverse Events will be tabulated and reported accordingly. The primary endpoint and all secondary endpoints will be analyzed based on both the ITT and PP population. All available data on the ITT patients who enrolled in the study will be included.

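### SAP 7.2 has no rule for ITT patients who never reach the end of a timed interval, so the procedural times will probably be medians conditional on success

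*SAP*

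**What the plan says.** Protocol 7.2 lists five carotid access intervals and seven intervals under time to final revascularization, introduced by "The following secondary outcomes will be collected and evaluated in all enrolled patients". One of them is "Last known well to final revascularization"; another, repeated in SAP 2, is "Arterial introduction of interventional tools to final revascularization".

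The analysis rule is a single sentence in SAP 7.2: "Continuous parameters will be summarized using descriptive statistics". The results go to Table 6.4.1, supported by a patient listing. SAP 2 and SAP 4 describe the data to be used; SAP 4 says "All available data on the ITT patients who enrolled in the study will be included".

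Entry to the ITT population (protocol 9 and 14.1, SAP 4) requires consent, eligibility and failed transfemoral therapy. It requires neither carotid access nor reperfusion. Protocol 10.3.4 adds: "The transcarotid intervention may be abandoned at the discretion of the treating operator", with the reason recorded in the patient records and case report forms.

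Failures have tables of their own: technical success in SAP 7.3 and core-lab revascularization success in SAP 7.4, both as counts and percentages. SAP 7.4 sets success at mTICI ≥2, whereas protocol 7.2 and SAP 2 set it at ≥2b. Neither document defines final revascularization.

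**The concern.** A mean or median can use only patients who have an end time. If patients without one simply leave the calculation, the time tables describe successes while the protocol promises all enrolled patients, and nothing in the SAP requires the table to show how many are missing.

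This matters because the study is single-arm with no hypothesis test, so its descriptive tables are its evidence. Protocol 23.5 names a shorter time to engage and recanalize the vessel as a possible benefit, and protocol 3.1 ties access delay to worse outcome. A reader who wants to know how soon a patient taken to transcarotid access can expect reperfusion would get an answer only for those in whom it worked.

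The practice is realistic. The protocol's background access time, from skin incision to carotid cannulation, "was 13 minutes in the ROADSTER study population (excluding aborted cases").

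**Working it through.** The documents give no time target, power calculation or expected time, so there is no figure of the plan's own to reproduce. The check has four steps.

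**1. Does another rule fill the gap?**
- SAP 5.1 deals with missing 90-day mRS and NIHSS only.
- The all-subject denominator in SAP 8 is for safety rates only.
- SAP 7.4 states no denominator and no rule for a missing post-procedure run.
- The SAP 2 and SAP 4 statements on available data say what is included, not how to treat a patient with no value.

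The times therefore have no rule.

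**2. How many patients could lack a time?** The inputs are from the direct carotid puncture series in protocol 3.2: reperfusion in 84% (16% failure) and 1 of 20 not catheterized (5%). Using these rates for this trial is an assumption. Expected number = N × f.

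| | N = 30 | N = 40 | Chance of at least one at N = 30 |
|---|---|---|---|
| No reperfusion, f = 0.16 | 4.8 | 6.4 | 1 − 0.84^30 = 99.5% |
| No catheterization, f = 0.05 | 1.5 | 2.0 | 1 − 0.95^30 = 78.5% |

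The first row applies only if the end event requires successful reperfusion.

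**3. How far is the success-only median from an all-patient median?** Let s be the proportion reaching the event, and rank failures as longest because they never reach it. Half of all patients have then reached the event at the 0.5/s quantile of the success times. With lognormal success times (assumed median 45 minutes, log-SD σ from 0.4 to 0.6):

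all-patient median = 45 × exp(σ × z(0.5/s))

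| s | 0.5/s | z | σ = 0.4 | σ = 0.6 |
|---|---|---|---|---|
| 0.95 | 0.526 | 0.066 | 46.2 | 46.8 |
| 0.84 | 0.595 | 0.241 | 49.6 | 52.0 |
| 0.75 | 0.667 | 0.431 | 53.5 | 58.3 |
| 0.65 | 0.769 | 0.736 | 60.4 | 70.0 |

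The success-only median is 45 minutes in every row. The rows at 0.75 and 0.65 are there for scale; the documents give no such rates.

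**4. Which way does the success-only median itself move?** Suppose every patient had a time, with median 45 and σ = 0.6, and a fraction f = 0.16 is then lost.
- Loss unrelated to time: the median stays at 45.
- The slowest 16% lost: the new median is the (1 − 0.16)/2 = 0.42 quantile, 45 × exp(−0.6 × 0.202) = 39.9 minutes.
- The fastest 16% lost: the new median is the (1 + 0.16)/2 = 0.58 quantile, 45 × exp(0.6 × 0.202) = 50.8 minutes.

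The direction depends on which cases fail.

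**Intervals affected.** Those ending in final revascularization are the most exposed, and those ending in catheterization or reverse flow less so. Hospital arrival to OR and arrival to neck incision are affected little or not at all. Clamp-to-unclamp time, although listed under time to revascularization, can exist in a failed case.

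**The case against.** The strongest reply is that the SAP nowhere restricts the times to successes; that reading comes from its silence. This is right, and the point here is only that a rule is missing and that success-only medians are the likely default.

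Second, final revascularization is undefined. If it means the last angiographic run whatever the grade, a completed but unsuccessful procedure has an end time, and mainly abandoned cases drop out. This also stands, and it makes the definition the first thing to settle.

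Third, failures are not hidden. Technical and revascularization success are tabulated, the listing is by patient, and reasons for abandonment are recorded. True, but no table combines success with time, and no count per interval is required.

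Fourth, access failure may be rare: acute device success with the predecessor device was 99.3% and 99.7%, in a different population. The access intervals may then hardly move. The larger figures concern reperfusion.

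Finally, the times are secondary and descriptive, with no test and no comparator in SAP Table 1. That limits the consequence but does not supply the rule.

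A reader might go further and infer that the reported times look faster the more cases fail, so that a worse device could show a better median. The documents do not support this. It holds only if the failures are the slow cases, which nothing in them establishes.

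**Conclusion.** The gap is real. Protocol 7.2 promises evaluation in all enrolled patients, ITT entry requires neither access nor reperfusion, abandonment is allowed, and SAP 7.2 does not say how a patient without an end time enters the summary. The probable product is a set of medians conditional on success that do not reflect failures.

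Against a median that ranks failures as longest, the understatement is about 5 to 7 minutes at 84% reperfusion and 1 to 2 minutes at 5% access failure. These sizes rest on the assumed 45-minute lognormal success times, on failure rates borrowed from one series of 20 patients, and, for the larger figure, on an end event that requires successful reperfusion. The absence of a rule rests on none of these.

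This should be corrected, as a cheap improvement to a secondary descriptive outcome. It does not affect the primary outcomes.

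**What to change.** 1. Define final revascularization as an end event, stating whether it requires a given grade and what stops the clock. Reconcile mTICI ≥2 in SAP 7.4 with ≥2b in protocol 7.2 and SAP 2.
2. In SAP 7.2, for all ITT patients and again for PP, add two cumulative proportions by time from neck incision: core-lab mTICI ≥2b, and reverse flow established. Show each as a curve or at prespecified times. Keep failed and abandoned cases in the denominator as not achieved. Do not censor them, because abandonment is informative.
3. For each interval report the number reaching and the number not reaching the end event. Keep the medians, labelled *among patients reaching the event, n = ..*.
4. In SAP 7.4 use all ITT patients as the denominator of the ITT analysis and count a missing post-procedure run as not revascularized.

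The cost is a short SAP addition and a little more analysis, from data already collected. The reported figures become slightly less favourable.

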7.3. Summary of Technical Success

The Technical Success Rate is defined as successful introduction of endovascular tools through the NOVIS Transcarotid NPS. Results will be tabulated using counts and percentages and presented in Table 6.4.2 entitled *Summary of Technical Success*. Results will be supported by the data presented in Listing 6.4.2 *Technical Success*, sorted by patient number and the date of procedure.

7.4. Summary of Revascularization Success

Revascularization Success is defined as an mTICI of ≥ 2 as assessed by the angiographic core lab. Results will be tabulated using counts and percentages and presented in Table 6.4.3 entitled *Summary of Revascularization Success*. Results will be supported by the data presented in Listing 6.4.3 titled *Angiographic Core Lab Adjudication of Postprocedural mTICI*, sorted by patient number and the date of procedure.

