Appendix 3. Abbreviations	49
Appendix 4. Definitions	51
Appendix 5. Patient Flow Diagram	54
Appendix 6. References.....	55

1 Protocol Summary

Title	Feasibility Study of the treatment of Acute Ischemic Stroke using the NOVIS Transcarotid Neuroprotection System In Transcarotid Embolectomy . (The NITE 1 Study)
Study Objective	To establish the feasibility and safety of the NOVIS Transcarotid Neuroprotection System when used for the transcarotid intervention of patients that have a failed transfemoral endovascular therapy in the case of anterior circulation strokes due to large vessel embolic occlusions.
Study Design	A prospective, multi-center, single arm feasibility study for the endovascular treatment of patients with acute ischemic anterior circulation strokes due to large vessel embolic occlusions using the transcarotid approach with flow reversal. Patients enrolled into the NITE 1 Study will have failed transfemoral therapy and will be followed immediately from post-op to 90 days.
Enrollment	A minimum of 30 and a maximum of 40 study patients will be enrolled into the per protocol population (reference Section 14.1 for definition).
Investigation Site Locations	Up to 8 sites in the United States of America.
Primary Outcomes	
 • Device-related Serious Adverse Events – vascular complications including dissection, pseudoaneurysm, hematoma, arteriovenous fistula, thrombus formation, embolization and any vascular complication that may be attributed to the device AND requires surgical repair, surgical wound revision, transfusion, etc. • Other Serious Adverse Events – permanent cranial nerve injury, new symptomatic ipsilateral hemorrhage and dissections related to ancillary devices. • Functional independence measured at 90-day mRS (proportion with mRS score 0-2)
Secondary Outcomes	
 • Carotid access time • Time to final revascularization • Device-related complications • Neurologic assessment at 90 days (proportion of patients with a nondisabling or disabling stroke according to NIHSS) • Technical success rates • Rates of revascularization success (mTICI \geq 2b)
Patient Population	Patients with acute ischemic anterior circulation stroke due to large vessel embolic occlusion who are candidates for endovascular therapy and in whom transfemoral therapy failed.

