14.2 Sample Size

A minimum of 30 and a maximum of 40 patients will be enrolled into the PP population and analyzed in this study. Enrollment in the ITT cohort will cease when 30 PP patients have been accrued. Additional patients beyond 30 who are successfully enrolled while waiting for the 30th PP patient to complete the 90-day follow-up period, will be analyzed in the cohort for which they qualify, whether PP or ITT. Enrollment will continue till a maximum of 60 patients are enrolled in the ITT population or the DSMB stops the study for safety reasons.

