- 2:** Partial Perfusion - The contrast material passes beyond the obstruction and opacifies the arterial bed distal to the obstruction; However, the rate of entry of contrast into the vessel distal to the obstruction and/or its rate of clearance from the distal bed are perceptibly slower than its entry into and/or clearance from comparable areas not perfused by the previously occluded vessel, e.g., the opposite cerebral artery or the arterial bed proximal to the obstruction
- 2a:** Only partial filling (< 50%) of the entire vascular territory is visualized
- 2b:** Filling of > 50% all the expected vascular territory is visualized, but the filling is slower than normal
- 3:** Complete Perfusion - Antegrade flow into the bed distal to the obstruction occurs as promptly as into the obstruction and clearance of contrast material from the involved bed is as rapid as from an uninvolved other bed of the same vessel or the opposite cerebral artery.

National Institutes of Health Stroke Scale (NIHSS)(Meyer et al. 2009)

The NIHSS is a graded neurological examination assessing consciousness, eye movements, visual fields, motor and sensory impairments, ataxia, speech, cognition and inattention. Often used to assess the severity of strokes based on the 11 components:

1. level of consciousness (1a: 0-3, 1b: 0-2 and 1c: 0-2)
2. best gaze (0-2)
3. visual fields (0-3)
4. facial palsy (0-3)
5. arm motor (0-4)
6. leg motor (0-4)
7. limb ataxia (0-2)
8. sensory (0-2)
9. best language (0-3)
10. dysarthria (0-2)
11. extinction and inattention (0-2)

These 11 components are then summed and the score correlates to stroke severity:

- 0 = no stroke symptoms
- 1-4 = minor stroke
- 5-15 = moderate stroke
- 16-20 = moderate to severe stroke
- 21-42 = severe stroke

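### SAP 7.4 sets revascularization success at mTICI ≥ 2, while the SAP's endpoint list and the protocol set it at ≥ 2b, so grade 2a would count as success

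*SAP*

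**What the plan says.** The cut-off for revascularization success appears in four places.

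- SAP 7.4, which names Table 6.4.3 and its supporting listing: "Revascularization Success is defined as an mTICI of ≥ 2 as assessed by the angiographic core lab".
- SAP Section 2, in the list of secondary endpoints to be summarized: "Rates of revascularization success assessed by angiographic core lab (mTICI \geq 2b").
- Protocol 7.2, with the same assessor and the same 2b cut-off as SAP Section 2.
- Protocol Section 1 (Protocol Summary): "Rates of revascularization success (mTICI \geq 2b").

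Protocol 23.5, on potential benefits, also describes successful reperfusion as mTICI 2b/3.

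Protocol Appendix 2 makes grade 2 (partial perfusion) a parent grade with two subdivisions. Grade 2a is "Only partial filling (< 50%) of the entire vascular territory is visualized". Grade 2b is filling of more than 50%, where "all the expected vascular territory is visualized, but the filling is slower than normal".

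On numbers of patients, SAP Section 4 "aims to recruit a minimum of 30 and a maximum of 40 patients in the PP population", and Protocol 14.2 adds that "Enrollment will continue till a maximum of 60 patients are enrolled in the ITT population".

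**The concern.** Adding or dropping the letter changes which patients are successes. On the Appendix 2 scale, ≥ 2 admits patients in whom less than half of the territory fills; ≥ 2b does not. SAP 7.4 is the table-level specification, so a programmer building Table 6.4.3 would naturally work from it.

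Protocol 14.3 rules out formal hypothesis testing, so the reported rates are themselves the result of the study. Both documents call for the secondary endpoints in the ITT and PP populations, and SAP Section 2 foresees use of the planned analyses in regulatory submissions, presentations and manuscripts. A rate built on ≥ 2 would reach those readers under the name of the ≥ 2b endpoint and would look at least as favourable as the rate the protocol promised.

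**Working it through.** The plan states no target rate, sample-size calculation or power for this endpoint, so there is no figure of its own to reproduce. The check compares the definitions and then sizes the difference.

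**Step 1: which grades each rule counts** (grades from Protocol Appendix 2)

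| Grade | Filling | SAP 7.4 (≥ 2) | SAP 2, Protocol 1 and 7.2 (≥ 2b) |
|---|---|---|---|
| 0 | none | failure | failure |
| 1 | minimal | failure | failure |
| 2a | < 50% | **success** | **failure** |
| 2b | > 50%, slow | success | success |
| 3 | complete | success | success |

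The two rules differ in grade 2a. A score recorded only as 2, with no subdivision, would also pass the rule in SAP 7.4, but it could not be placed under ≥ 2b.

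**Step 2: direction.** The set {2b, 3} lies inside {2a, 2b, 3}. On the same patients and the same denominator, the ≥ 2 rate is therefore equal to or above the ≥ 2b rate.

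**Step 3: size per patient.** Let k be the number of patients counted only under ≥ 2, and N the denominator. The difference is 100 × k/N percentage points. The values of N are the PP minimum (30), the PP maximum (40) and the ITT maximum (60).

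| k | N = 30 | N = 40 | N = 60 |
|---|---|---|---|
| 0 | 0 | 0 | 0 |
| 1 | 100/30 = 3.3 | 100/40 = 2.5 | 100/60 = 1.7 |
| 2 | 6.7 | 5.0 | 3.3 |
| 3 | 10.0 | 7.5 | 5.0 |

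The documents do not give k; the rows only show how the difference scales.

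**Step 4: would the two rules differ in practice?** This step needs the share p of patients who end at 2a, which the documents do not give. I assume 5% to 20%, purely as an illustration. The chance that at least one patient is 2a is 1 − (1 − p)^N.

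| Assumed p | N = 30 | N = 40 | N = 60 |
|---|---|---|---|
| 5% | 1 − 0.95^30 = 0.785 | 0.871 | 0.954 |
| 10% | 1 − 0.90^30 = 0.958 | 0.985 | 0.998 |
| 20% | 1 − 0.80^30 = 0.999 | > 0.999 | > 0.999 |

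In expectation, the overstatement equals p itself: 5 to 20 points over the assumed range.

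**The case against.** The strongest reply is that this is a slip that nobody would act on. One sentence stands against three, one of them in the same SAP with the same assessor, and nothing in either document argues for ≥ 2. A careful programmer would query it. The endpoint is secondary, has no hypothesis test and is absent from the planned external comparisons in SAP Table 1, so no stated decision depends on it. Listing 6.4.3 gives the core-lab adjudication by patient, so the ≥ 2b rate could be recounted. A character lost in converting the PDF to text cannot be wholly ruled out either.

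Much of this stands, and it limits the weight of the point. It does not remove it. An analysis plan should not depend on someone noticing that its table specification disagrees with its endpoint list. A listing does not correct a wrong table, and it allows a recount only if it shows 2a and 2b separately, which SAP 7.4 does not say. The letter survives in the other three places and the sentence in SAP 7.4 is otherwise intact, so a conversion loss is unlikely; a look at the signed SAP would settle it.

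Two qualifications on size are fair:

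- The points per patient assume that every patient in the population is in the denominator. The SAP fixes an all-subjects denominator only for safety events (Section 8), and Protocol 10.3.4 allows the intervention to be abandoned. SAP Section 4 also allows enrollment to stop before 30 PP patients. A smaller denominator would make each 2a patient count for more.
- A score recorded only as 2 might in truth be a 2b, so counting it need not be an overstatement. Nothing in the documents suggests that the core lab will report such a score.

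**Conclusion.** The concern holds. SAP 7.4 contradicts the SAP's own endpoint list and the protocol, and as written it counts grade 2a as success. The bias can only favour the device or be nil. It is 3.3, 2.5 or 1.7 points per 2a patient at N = 30, 40 or 60, taking the full population as denominator. No total is claimed, because the share of 2a results is not in the documents. Sample size and error rates are untouched. This should be corrected because it sits in the section that governs the reported table, but it does not threaten the study's primary conclusions.

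**What to change.** In SAP 7.4, define revascularization success as a core-lab mTICI of 2b or 3 (≥ 2b), in line with SAP Section 2, Protocol 7.2 and the Protocol Summary. State that Listing 6.4.3 shows 2a and 2b as separate grades, so that the table can be checked against it; this second change is a safeguard and less essential than the first.

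The cost is one line of the SAP and a listing format. The Appendix 2 scale already separates the two grades, so no new data and no further core-lab reading are needed. The only downside is a success rate that may be less favourable than the present wording would give.
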